“Observations Regarding Infection Risk in Lower-Extremity Wound Healing by Second Intention,” by Molina et al, was a retrospective study of 555 patients treated with MMS on the lower extremities with wounds left for second intention healing was conducted investigating the rate of infection and pathogenic organisms. Of 555 patients, 24 patients (4.3%) returned to clinic with culture-positive wound infections within 90 days of surgery. The majority (n= 15, 63%) of infections were caused by *Staphylococcus aureus*.

“Oral Antibiotics Versus Topical Decolonization to Prevent Surgical Site Infection After Mohs Micrographic Surgery—a Randomized, Controlled Trial,” by Cherian et al was a randomized, controlled trial with 693 patients. Nasal carriers of *S. aureus* were randomized to receive topical decolonization with intranasal mupirocin twice daily plus 4% chlorhexidine gluconate body wash daily for 5 consecutive days before surgery or pre- and postoperative doses of oral cephalexin. Nine percent of patients receiving oral antibiotic prophylaxis and none of the patients receiving topical decolonization developed early SSI (p = .003).

“Randomized Controlled Trial of Preoperative Topical Decolonization to Reduce Surgical Site Infection for *Staphylococcus aureus* Nasal Swab-Negative Mohs Micrographic Surgery Patients,” by Smith et al was a randomized controlled trial of *S. aureus* nasal swab-negative patients. Five days before Mohs surgery topical decolonization with nasal mupirocin and chlorhexidine body wash was started. The control group had no intervention. Results demonstrated the infection rate in the intervention group was 2% and that of the control group was 4%.

A.2. Study Design

This study is a prospective, randomized trial. Patients will be randomly placed into one of two arms. The experimental group will receive decolonization with mupirocin 2% ointment to the nares and chlorhexidine washes to the skin folds and lower extremities. The control group will not receive any pre-operative decolonization. This is not a pilot study.

A.3. Intervention

Patients in our experimental group will apply mupirocin 2% ointment to each nostril twice daily five days prior to surgery. Chlorhexidine will be applied to the skin folds and lower extremities during the five

consecutive showers prior to surgery. Patients will be instructed to let the chlorhexidine sit for one minute prior to rinsing.

A.4. Allocation to Interventional Group

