Patients will be randomized to either the control (standard of care) group or the experimental (decolonization) group. A log will be kept allowing for randomization of patients into control arms. The log will alternate between study and control group. The patient will be entered into the log in the order that their telehealth was completed, which will determine their study group.

A.5. Sample Size Calculation

Our previous study determined a surgical site infection rate of ~10% in lower extremity surgical wounds healing by second intention. Given our assumption that the intervention would reduce the incidence to 5%, the minimal sample size necessary to detect a 5% absolute difference between the intervention and control group would be 424 per group for a total of 848 subjects. We plan to enroll subjects at 10 study centers in order to be able to reach the sample size required for adequate power.

A.6. Data Analysis Plan

Fisher's exact test will be used to compare categorical variables.

B. Subject Population

B.1. Description of Subject Population

This study will target any patients undergoing Mohs micrographic surgery or surgical excision on the lower extremities that will heal by second intention as determined by the surgeon performing the procedure.

B.2. Inclusion Criteria

- Individuals undergoing surgical treatment for skin cancer on the lower extremities.
- Postoperative wounds healing by second intention
- Must be at least 18 years old.

B.3. Exclusion Criteria

- Any individual taking antibiotics during the peri-operative period or post-operative period (for a reason other than surgical site infection)
- Patients with known intolerance or hypersensitivity to mupirocin or chlorhexidine.
- Patients that are currently pregnant or attempting to become pregnant.
- Patients with a history of *Staphylococcus aureus* infections.
- Patients with a history of heart valve or joint replacement requiring pre-operative antibiotics.

B.4. Eligibility Screening

All patients referred to our clinic for Mohs micrographic surgery or surgical excision will be screened for inclusion in this study. The scheduling staff will alert study physicians of any patient who is being scheduled for surgery on the lower extremity. Once flagged, a study physician will review the location and deem if patient an appropriate candidate for the study.

B.5. Recruitment

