The dermatologic surgery staff will be educated on the inclusion criteria for this study. Patients referred to our office with lower extremity lesions will be flagged by the dermatologic surgery staff.

Once flagged, the patient's information will be sent to study personnel who will verify that the patient meets eligibility criteria. A physician will then contact the patient for a pre-operative telephone consultation to discuss participation in the study.

B.6. Informed Consent

At the pre-operative consultation, the study will be described to the subjects by the physician enrolling them. Subjects will be assured that their participation is voluntary and their level of care will not change based on their decision. They will have time to review the consent form and be able to ask any questions prior to signing the consent form.

If the pre-operative consultation is conducted virtually, the investigators will verbally explain the study and provide subjects with a copy of the consent materials electronically (via REDcap or other means) or by mail. Prior to enrollment, attempts will be made to obtain an electronic (if acceptable per institutional policies) or hand-written signature from subjects. However, if the subject is willing to participate but obtaining the signature is logistically burdensome, verbal consent will be accepted and the subject enrolled. A waiver of written documentation of consent [21 CFR §56.109(c)(1) and 45 CFR §46.117(c)(2)] will be requested of the reviewing IRB in order to enroll the subject on the study. The consent form will be reviewed during the pre-operative visit to discuss the research and ensure that the subject is fully informed. Subjects that are mailed a copy of the consent form will be asked to sign and bring it with them on the day of their surgery. Patients that sign the REDcap consent form will be asked to sign a hard copy on the day of their surgery.

C. Study Procedures

C.1. Summary of Methods and Procedures

Patients meeting eligibility criteria will be approached at their pre-operative consultation and asked to participate. After providing informed consent, as previously described, subjects will be randomly placed into one of the two arms.

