Once enrolled, subjects in the experimental group will be prescribed mupirocin 2% ointment and chlorhexidine wash. Instructions for decolonization will be provided to the subjects in a "pre-procedure handout and a medication log in order to help them perform and track the decolonization protocol sufficiently. Subjects in the experimental group will follow decolonization procedures for 5 days prior to surgery.

On the day of their procedure, all subjects will be asked to fill out a demographic survey to evaluate their risk of developing infection. The demographic survey sheet will record the patients' age, sex, prior *Staphylococcus aureus* infections, medications, BMI over 25, smoking status, number of showers per week, and medical history of diabetes, immunosuppression, peripheral vascular disease, and nutritional deficiency. Patients' answers will be recorded in a protected, unidentified database.

Following surgery, all subjects will be asked to send in a picture of their surgical site during the postoperative period at weeks 2 and 4. Patients will submit photos of their surgical site via the Cooper RedCap system. They will receive an email prompting them to upload their photos at these points. Photographs will be evaluated by a study physician upon receipt. After that one month, the patient will be informed that they no longer need to send in any more photos.

Any patient who develops symptoms of an infection or has concerning findings on the pictures will be instructed to schedule a follow up appointment for evaluation. At this visit, their wound will be swabbed for the causative pathogens. The results from the wound culture will be shared with the patients and, if positive for pathogenic bacterial growth, will be started on antibiotics for treatment of their surgical site infection.

Subjects that do not require a follow up appointment will be followed up with a call at one month post-surgery. We will ask these patients if they developed a wound infection or if they had any issues with their surgical site.

C.2. Study Visits

On the day of the procedure, the patient will be given an envelope containing a hard copy of their official consent form to sign (if they did not bring their copy from home) and a demographic survey sheet.

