It is not standard of care for patients undergoing Mohs micrographic surgery or excision on the lower extremities to decolonize with mupirocin 2% ointment and chlorhexidine. Although not standard of care, is commonly utilized by dermatologic surgeons for patients with a history of *Staphylococcus aureus* infections.

It is not standard of care for patients to complete a demographic surgery prior to their procedure.

C.7. Subject Withdrawal

Subjects can withdraw from the study at any time with no penalty by contacting the study team. Data that has already been collected will be retained, but not further data will be collected for research purposes.

If any patient experiences side effects to mupirocin ointment or chlorhexidine, such as burning, itching, or dryness at the application site, they will be instructed to alert the study staff. A physician from the study staff will then have a telephone consult with the patient about the side effects they are experiencing, and based on the physician evaluation, will either be asked to discontinue the medication and be removed from the study, or be counseled that it is safe to resume the study. Any patient that experiences side effects will be counseled that they may withdraw from the study at any time.

D. Additional Human Subject Considerations

D.1. Vulnerable Populations

There are no vulnerable populations involved in this study.

D.2. Economic Impact on Subjects

The only cost patients may have is the cost for the chlorhexidine and mupirocin ointment, depending on their insurance coverage.

D.3. Compensation

Patients will not be compensated for participating in this research study.

D.4. Treatment for Research-Related Injuries

The physicians that perform the procedures will provide treatment for any research-related injuries, such as infection treatment.

D.5. Sharing Study Results

If a wound culture is obtained from a patient, the results from the culture will be shared with them.

D.6. Risks

The patients involved in this study may encounter the following risks:

1. Patients have the possibility of developing side effects to the chlorhexidine and mupirocin treatment, such as burning, stinging, or dryness in the treatment area.
2. Patients may feel uncomfortable answering questions on the demographic questionnaire.
3. There is a risk of confidentiality if medical information or identity are obtained by someone other than the investigators, but precautions will be taken to prevent this from happening.

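### C.7 can remove allocated patients from the experimental arm only and conflicts with the follow-up promised in C.2 and D.6.1; B.3's post-operative antibiotic exclusion carries a lesser form of the same risk

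*Protocol*

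**What the plan says.** **Order of events.** Eligibility is checked before the pre-operative call by "study personnel who will verify that the patient meets eligibility criteria" (B.5). The arm follows from the log: "The patient will be entered into the log in the order that their telehealth was completed, which will determine their study group" (A.4). C.1 puts this after consent: "After providing informed consent, as previously described, subjects will be randomly placed into one of the two arms".

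**Exposure.** "Subjects in the experimental group will follow decolonization procedures for 5 days prior to surgery" (C.1). For the other arm, "The control group will not receive any pre-operative decolonization" (A.2).

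**Removal.** C.7 sends a patient with product side effects to a physician's telephone consultation. The patient then "will either be asked to discontinue the medication and be removed from the study", or is told it is safe to carry on. A separate paragraph of C.7, on subjects who choose to withdraw, keeps the data already held and ends further collection.

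**Follow-up.** C.2 asks every enrolled patient in either group for photographs at 2 and 4 weeks, and provides a one-month call for those without infection: "We will ask these patients if they developed a wound infection or if they had any issues with their surgical site". D.6.1 item 4 says that study personnel will contact every enrolled patient one month after the procedure about complications at the site.

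**Antibiotics.** B.3 lists as an exclusion "Any individual taking antibiotics during the peri-operative period or post-operative period (for a reason other than surgical site infection".

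**The concern.** A randomized comparison rests on comparing the groups as they were allocated. The C.7 removal is triggered by exposure to the study products, so it has no counterpart among controls. If the patients removed differ in infection risk from those who stay, the remaining experimental group no longer matches the control group. Because the products are used before surgery and infection is observed afterwards, a removed patient will usually have no outcome on file. If follow-up stops as well, that outcome is not there for any later analysis to use.

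The antibiotic criterion is a weaker case of the same kind. Courses that are ongoing or planned can be screened out under B.5. A course begun after allocation can only concern a patient who already has an arm. The protocol does not say what then happens, and 10 centers (A.5) may read an exclusion criterion differently. No masking is described and controls are untreated, so handling could also differ by arm.

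**Working it through.** **1. The plan's own figure.** A.5 gives 10% against 5% and 424 per group. Alpha and power are not stated; I assume two-sided 0.05 and 80%. The arcsine formula gives h = 2·asin(√0.10) − 2·asin(√0.05) = 0.1925 and n = 2·((1.960 + 0.842)/h)² = 423.7, so 424 reproduces. For the test named in A.6 (Fisher, full enumeration), power at 424 per group is 75.8%. A.5 states no allowance for removals.

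**2. The passages side by side.**
- The sequence is eligibility check, consent, allocation, 5 days of products (experimental arm only), surgery, then photographs and call. The C.7 trigger lies between allocation and outcome, in one arm.
- C.1 prescribes the products to subjects who are already enrolled. A patient removed under C.7 is therefore an enrolled patient, whom C.2 and D.6.1 item 4 cover as written.
- C.7's sentence ending data collection stands in the paragraph on voluntary withdrawal. The paragraph on physician removal says nothing about data. Extending the sentence to removed patients is a natural reading but not a stated one, and it is this reading that conflicts with C.2 and D.6.1.

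**3. Size of a false gap.** Assume no true effect, with 10% infection in both arms as allocated. Let k patients leave the experimental arm with infection risk q. The retained rate is (42.4 − kq)/(424 − k), and control minus experimental is k(q − 0.10)/(424 − k). The removal rates and q are assumptions; the protocol gives neither.

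| Removed (assumed) | k | q = 0% | q = 10% | q = 20% |
|---|---|---|---|---|
| 2% | 8 | −0.19 points | 0 | +0.19 points |
| 5% | 21 | −0.52 | 0 | +0.52 |
| 10% | 42 | −1.10 | 0 | +1.10 |

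A positive gap looks like benefit. At the extremes of q, the chance of a significant Fisher result is about 4.4% to 4.5%, 5.1% and 7.1% to 7.4%, against 3.8% with no removals. Part of that rise comes from the unequal group sizes: at average risk the figure is already 4.3% to 4.4%.

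**4. What keeping the patients costs in power.** Suppose those who stop the products get no benefit (10% risk, assumed) and all other experimental patients have 5%. The kept experimental rate is (0.10k + 0.05(424 − k))/424.

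| k | Kept: rate | Kept: Fisher power | Removed: group sizes | Removed: Fisher power |
|---|---|---|---|---|
| 0 | 5.00% | 75.8% | 424 v 424 | 75.8% |
| 8 | 5.09% | 73.8% | 424 v 416 | 77.6% |
| 21 | 5.25% | 70.5% | 424 v 403 | 77.1% |
| 42 | 5.50% | 64.9% | 424 v 382 | 75.0% |

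Values above 75.8% in the last column reflect the discreteness of Fisher's test with unequal groups, not a real gain.

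**5. Antibiotic users.** Assume 10% of each arm uses non-SSI antibiotics and the others stay at 10% and 5%. If users are kept, the result depends on their own risks:
- 0% in both arms: 9.0% v 4.5%, power 70.4%
- 2.5% in both arms: 9.25% v 4.75%, power 68.9%
- 5% in both arms: 9.5% v 5.0%, power 67.4%
- 5% v 2.5%: 9.5% v 4.75%, power 73.2%
- the same as everyone else, 10% v 5%: power 75.8%

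If users are excluded, 382 per group at 10% v 5% gives 71.4%.

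**The case against.** **Follow-up is already promised.** C.2 and D.6.1 make no exception for patients who stopped the products. This stands. A reader might infer that the outcomes of removed patients are certainly lost and cannot be recovered. The documents do not support that; they show a conflict to be resolved. Nor do they settle it the other way, because C.7 speaks of removal from the study and not merely from the products.

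**B.3 orders no removal.** This stands too. A reader might infer that every allocated patient who starts a new course is dropped. No passage says so, and none suggests that such use differs by arm. That is why the antibiotic criterion is secondary here.

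**The exposure is narrow.** Removal is one of two results of a physician's judgement, known intolerance is excluded (B.3), and patients are instructed how to limit irritation (D.6.1). The documents give no reason why irritation should track infection risk. All of this limits the size, but it does not make the rule apply to both arms.

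**The numbers are small.** At 2% to 5% removal the gap is at most about 0.5 points. A reader might reach for a worse case: 10% removed at 30% risk leaves (10 − 0.10 × 30)/0.90 = 7.8%, a 2.2-point gap. Nothing in the documents supports a threefold risk in these patients.

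**The analysis set may be in a SAP.** It may, and its absence from the protocol is not the complaint. The complaint is about a removal rule that the protocol itself states. If follow-up does end, a choice of analysis set cannot supply the outcomes.

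**Conclusion.** The point holds and should be acted on. C.7 states a removal after allocation that can affect only the experimental arm, usually before any infection outcome. Read as also ending data collection, it contradicts C.2 and D.6.1 item 4, and these passages must be reconciled. B.3 adds a lesser ambiguity for antibiotic courses begun after allocation.

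Neither the size nor the direction of bias can be fixed from the document. Under the assumed removal rates and risks it is modest beside the planned 5 points, and it vanishes if removed patients carry average risk. The case therefore rests on keeping the allocated groups intact at little cost. It rests neither on a demonstrated large bias nor on power, which the change can lower.

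**What to change.** - **C.7:** separate stopping the study products from leaving the study. The clinical decision to stop stays exactly as written. State that patients who stop continue with the photographs and the one-month call unless they themselves withdraw, and that the sentence ending data collection applies only to those who withdraw. This brings C.7 into line with C.2 and D.6.1.
- **A.6:** state that these patients are analysed in their allocated arm.
- **B.3:** limit the antibiotic criterion to use known, ongoing or planned at allocation. Record later non-SSI use as data, for example by one question put to all patients at follow-up (C.1, C.2), without removing the patient.

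**Cost.** Wording in three sections, one added question, and photographs and a call for the few who stop, which C.2 and D.6.1 already promise. The statistical cost is dilution. Fisher power falls from 75.8% to about 74%, 70% or 65% if 2%, 5% or 10% of the experimental arm stop and get no benefit. With antibiotic users kept, it lies at about 67% to 76% depending on their risks. All these rates are assumed.

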All patients enrolled in the study, regardless of group, , will send in a picture of their surgical site 2 weeks and 4 weeks after their surgery. Any patient who develops symptoms of an infection or has concerning findings on the pictures they send in will be instructed to schedule a follow up appointment for evaluation. Here, their wound will be swabbed for the causative pathogens.

Any subject who develops an infection will be identified by the pictures sent to the physician or the patients' concern for infection. During this visit, a wound culture will be collected to determine the responsible pathogen. Wound culture results will be recorded within the data collection sheet.

All patients that do not develop an infection will be followed up with a call at one month. We will ask these patients if they developed a wound infection or if they had any issues with their surgical site.

C.3. Study Duration

Subjects will be asked to participate in this study for 1 month after their surgery. The overall study should take a little over a month for the treatment group since they will also have to pretreat the surgical site.

C.4. Drugs, Biologics, and Devices

All drugs used on this study are FDA approved and will be used according to label. The research is not intended to be reported to the FDA as a well-controlled study in support of a new indication for use for the drugs, nor is it intended to support a significant change in the labeling for the drugs.

Mupirocin 2% ointment: Indicated for the eradication of nasal colonization with methicillin-resistant *Staphylococcus aureus* (MRSA) in adult and pediatric patients (aged 12 years and older) and healthcare workers as part of a comprehensive infection control program to reduce the risk of infection among patients at high risk of MRSA infection during institutional outbreaks of infections with this microorganism.

Clorhexidine wash: Indicated for use as an antimicrobial skin cleanser helps reduce bacteria that potentially can cause disease; for skin wound and general skin cleansing; surgical hand scrub; personnel hand wash; and preoperative skin preparation.

C.5. Safety Evaluation (if applicable)

In the case that an infection develops at the surgical site, a bacterial culture will be taken to identify the causative pathogen. This will allow the physician to properly treat the infection with appropriate antibiotics.

C.6. How Participation Differs from Standard-of-Care

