D.6.1. Minimizing Risks

The following is being done to minimize the above risks from occurring:

1. Patients can decline to answer any of the questions on the questionnaire or withdraw from the study at any point.
2. All patients will receive treatment if they develop skin infections.
3. All measures will be taken to avoid breach of PHI. All personal health information will be de-identified from the study data. All data will be stored on a password-protected computer that will not leave the Cooper Center for Dermatologic Surgery. Only study personnel will have access to the computer.
4. All patients will be provided with a telephone number that will allow them to reach a physician in our practice should they have any questions or develop symptoms concerning for infection. They will be scheduled for an appointment if the evaluating physician is concerned for possible infection. Additionally, all patients enrolled will be contacted directly by study personnel one month after the procedure to evaluate if they had or are currently having any complications at the surgical site.
5. Subjects will be screened to avoid enrollment of a patient who may be sensitive to mupirocin or chlorhexidine.
6. Subjects will be provided instructions on how to properly apply mupirocin and chlorhexidine to reduce skin irritation

D.6.2. Privacy Protections

The patient is under no obligation to discuss their involvement with anyone at the office outside of study personnel. They can schedule appointments without mentioning they are involved in a research study.

D.7. Benefits

There are no direct benefits to patients who are involved in this study. This data has the potential to change the standard of care for patients receiving dermatologic surgeries on the lower extremities healing by second intention. Currently, decolonization is not a standard of care before procedures. By showing this process reduces the rate of post-operative infections, physicians could implement this into their practice, leading to reduced morbidity, improved patient outcomes, and reduced healthcare cost burden from surgical site infections.

E. Safety Monitoring

Data and Safety Monitoring Plan

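### Section C.7 removes patients told to stop mupirocin or chlorhexidine for side effects, which can only happen in the decolonization arm and conflicts with follow-up of all enrolled patients

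*Protocol*

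**What the plan says.** Section C.7 (Subject Withdrawal) has two parts. The first covers patients who choose to withdraw: "Data that has already been collected will be retained, but not further data will be collected for research purposes". The second begins "If any patient experiences side effects to mupirocin ointment or chlorhexidine, such as burning, itching, or dryness at the application site" and provides for a telephone consultation with a study physician. After it, the patient "will either be asked to discontinue the medication and be removed from the study", or is counseled that continuing is safe. No third outcome is given.

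Exposure to the products is confined to one arm:
- Section A.2: "The control group will not receive any pre-operative decolonization".
- Section C.1: "Once enrolled, subjects in the experimental group will be prescribed mupirocin 2% ointment and chlorhexidine wash", and "Subjects in the experimental group will follow decolonization procedures for 5 days prior to surgery".

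Follow-up is described without exceptions:
- Section C.2: "All patients enrolled in the study, regardless of group", send photographs of the surgical site at weeks 2 and 4.
- Section D.6.1, item 4: "all patients enrolled will be contacted directly by study personnel one month after the procedure".

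**The concern.** Stopping a treatment and leaving a trial are separate events, and C.7 merges them. Its trigger is a reaction to products that controls are never assigned, so the loss falls on one arm only, follows allocation and is caused by the allocated treatment.

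If removal ends follow-up, the trial compares decolonization patients who were not stopped for intolerance with all controls. That comparison is biased whenever the removed patients differ from the rest in infection risk, for example because of their skin condition. The direction cannot be known in advance. A later analysis plan can define who is analyzed, but it cannot supply outcomes that nobody collected.

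The conflict with C.2 and D.6.1 also matters in practice. With 10 centers planned (A.5), some could follow C.7 and others the general follow-up text.

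**Working it through.** **Reading the passages together**

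1. Who can meet the trigger? Only patients assigned mupirocin and chlorhexidine, which is the decolonization arm (A.2, C.1).
2. When? The products are prescribed after enrolment and used in the five days before surgery (C.1), so a removal during that course comes before any wound outcome exists.
3. What happens to the outcome? C.2 and D.6.1 include all enrolled patients, while C.7 takes some of them out. Neither side refers to the other. Read naturally, removal from the study ends follow-up, but the protocol does not say so explicitly.

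**Inputs**

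- From A.5: about 10% infection in controls, 5% with the intervention, 424 per group.
- From A.6: Fisher's exact test.
- Assumed, because the protocol does not state them: two-sided 5% level, 80% power, share removed *s*, infection risk of the removed *r*.

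**The plan's own figure**

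The arcsine formula is n = 2 × ((1.960 + 0.842)/h)², with h = 2·arcsin√0.10 − 2·arcsin√0.05 = 0.1925. It gives 423.7, so 424 per group, as stated.

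**Size of the bias with no true effect**

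The whole decolonization arm has 10% risk. The rate among those who remain is (0.10 − s·r)/(1 − s). For s = 0.05 and r = 0.20 this is (0.10 − 0.01)/0.95 = 9.47%, a false benefit of 0.5 points.

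| Share removed (patients) | Risk of removed | Rate in those remaining | False benefit (points) |
|---|---|---|---|
| any | 10% | 10.00% | 0 |
| 2% (8) | 20% | 9.80% | 0.2 |
| 5% (21) | 20% | 9.47% | 0.5 |
| 10% (42) | 20% | 8.89% | 1.1 |
| 10% (42) | 30% | 7.78% | 2.2 |
| 2% (8) | 5% | 10.10% | −0.1 |
| 5% (21) | 5% | 10.26% | −0.3 |
| 10% (42) | 5% | 10.56% | −0.6 |

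**Chance of a false significant result**

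This comes from full enumeration of two binomials: 424 controls at 10% against 416, 403 or 382 remaining patients at the rates above, with two-sided Fisher's exact p ≤ 0.05. Fisher's test is discrete, so its error rate changes with the arm sizes even without bias. The third column isolates that effect.

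| Case | False-positive rate | Same arm sizes, no bias |
|---|---|---|
| No removal, 424 v 424 | 3.8% | 3.8% |
| 2% removed at 20% risk | 4.5% | 4.3% |
| 5% removed at 20% risk | 5.1% | 4.4% |
| 10% removed at 20% risk | 7.4% | 4.4% |
| 10% removed at 30% risk | 17.9% | 4.4% |

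**Power**

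By the normal approximation, power for 10% v 5% is 79.0% with 424 per arm. It is 78.6%, 77.9% and 76.5% when 2%, 5% and 10% of the decolonization arm are removed. Lost power is a minor matter; the possible bias is the main one.

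**The case against.** The strongest reply has four parts.

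- **Ambiguity rather than contradiction.** C.2 and D.6.1 are general statements and C.7 could be read as a specific exception. The sentence ending data collection is written for patients who withdraw by choice, not for those a physician removes. D.6.1 might still bring removed patients a one-month call, and E.1 follows adverse events to resolution. This stands in part: the loss of outcome rests on the natural meaning of removal and is not separately stated. It does not rescue the text, because a center that follows C.7 as written will lose these outcomes.
- **The error-rate comparison is partly an artefact.** Against arms of equal size with no removal, the rise looks like 0.7 points at 2% removed and 1.3 at 5%. Against the same unequal arms without bias it is about 0.2 and 0.7. This is correct, and the table shows both. At 10% removed, most of the rise is due to bias.
- **The larger cases rest on unsupported inputs.** The protocol gives no removal share and no link between irritation and leg-wound infection. Removal needs a physician's advice to stop, and D.6.1 provides for sensitivity screening and application instructions. This stands: the share should be low, and at 2% to 5% the shift is −0.3 to +0.5 points against a planned difference of 5.
- **The analysis set may be in an SAP that is not at hand.** That is possible, and its absence from the protocol is not criticized here. Whether outcomes are collected is a protocol matter, and an SAP cannot repair it.

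**Conclusion.** The concern holds. Followed as written, C.7 causes treatment-related removal from one arm after allocation and before the outcome, and it does not agree with the follow-up of all enrolled patients in C.2 and D.6.1.

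The likely size is modest. With the removed at 20% risk, the false benefit is 0.2 to 0.5 points for 2% to 5% removed and 1.1 points for 10%; the extreme case of 10% removed at 30% risk gives 2.2 points. It is zero at equal risk and reversed at lower risk. All removal shares and risks are assumptions, as is the two-sided 5% level, and the bias arises only if removal ends outcome collection. The defect is worth correcting because it is avoidable, cannot be undone afterwards and costs almost nothing to remove.

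**What to change.** In C.7, delete the words that remove the patient from the study. State instead that patients who stop the products because of side effects stay in follow-up for the week 2 and week 4 photographs and the one-month contact, unless they themselves withdraw, and are counted in their allocated arm. C.7 then agrees with C.2 and D.6.1.

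The physician's decision on stopping a product, the criteria in B.2 and B.3, and the rule on patients' own withdrawal stay as they are.

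The cost is one sentence. No new procedure is needed, because the photographs and contact are already planned for every enrolled patient. The one drawback is that including patients who stopped early may slightly dilute the estimated effect. That estimate still describes what offering decolonization achieves, which is the change in practice that section D.7 has in view.
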